6.5.2 Adverse Events, Serious Adverse Events, and Deaths

All AEs and SAEs will be reported until 30 days after the last dose of investigational product(s) and will be followed until resolution or until condition stabilizes. AEs and SAEs will be coded using MedDRA v24.0 or later and graded by the Investigator according to the NCI CTCAE v5.0 or later.

Summaries of adverse event will in general focus on treatment emergent adverse events (TEAEs) which is defined as adverse event that occurs or worsens on or after first dose of investigational product and up to 30 days after the last dose.

Subject incidence of the following events will be tabulated:

- All TEAEs
- SAEs
- SAEs not associated with transfusion
- Treatment-related TEAEs

- Treatment-related SAEs
- Grade 3 or 4 TEAEs
- TEAE leading to treatment discontinuation, dose reduction, dose interruption

Listings of TEAEs leading to IP discontinuation, and SAEs will be provided. Listings will be sorted by patient ID and study day; All AE listings will include patient ID, study day, SOC, PT, reported term, AE onset date, AE end date, outcome, duration, relationship to drug, action taken, and severity.

The incidence of death will be summarized by cause of death and on-study status at time of death (within 30 days of last dose vs. more than 30 days after last dose). Patient death listings will include all death data available including date of death, cause of death and any AEs resulting in death.

6.5.3 Clinical Laboratory Evaluation

Laboratory data will be summarized in tables using descriptive statistics for baseline and each cycle/visit. Descriptive statistics will be calculated on both the actual value and the change from baseline. Additionally, clinically significant abnormalities in laboratory results will be summarized for the post-baseline cycles/visits using frequencies and percentages. Shifts in CTCAE grade between baseline and subsequent visits will be summarized as well.

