8.9. Clinical Laboratory Assessments

Clinical laboratory assessments will be performed by each institution's local laboratory and must be resulted and evaluated prior to administration of the study drug. The laboratory variables in [Table 6](#) will be collected in accordance with the Schedule of Events ([Table 1](#)).

Table 6: Clinical Laboratory Assessments

Serum or Plasma Chemistry:	Sodium Potassium Chloride Calcium Magnesium Phosphorous Glucose	Total Bilirubin Aspartate aminotransferase Alanine aminotransferase Alkaline phosphatase Albumin Total protein Creatinine
Hematology:	Red blood cell count Hemoglobin Hematocrit Platelet counts White blood cell count with differential (reported as absolute counts), where possible Total neutrophils 
• Lymphocytes• Monocytes• Eosinophils• Basophils	
Coagulation:	International normalized ratio Partial thromboplastin time Activated partial thromboplastin time	
Pregnancy Test:	In women of childbearing potential only: serum β -human chorionic gonadotropin pregnancy test, urine, or urine dipstick	

All clinically significant unscheduled laboratory results will be recorded, and all clinically significant laboratory results (scheduled and unscheduled) obtained during the study period will be reported as AEs (e.g., Grade ≥ 2 aspartate aminotransferase, alanine aminotransferase, or serum bilirubin).

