6.7 Exploratory Biomarker Analysis

7. CHANGES TO THE ANALYSES PLANNED IN THE PROTOCOL

8. LIST OF PLANNED TABLES

Category	Title
Disposition	Summary of Subject Disposition
Demography and Baseline Characteristics	Summary of Demographics
	Summary of Baseline Disease Characteristics
Medical History	Summary of Medical History
Prior Cancer Therapy	Summary of Prior Anticancer Medications
	Summary of Prior Anticancer Radiotherapy
	Summary of Prior Anticancer Surgical Therapy
	Summary of Biomarkers
Concomitant Medications	Summary of Concomitant Medications
Study Medication	Summary of Treatment Exposure
	Summary of Treatment Dose Reduction
	Summary of Treatment Dose Hold
Efficacy	Summary of Objective Response Rate
	Summary of PFS
	Summary of Disease Control Rate
	Summary of GMI
Safety	Summary of Overall Safety
	Incidence of TEAE by Preferred Term
	Incidence of TEAE by System Organ Class, Preferred Term, and Grade
	Incidence of Serious Adverse Events by Preferred Term
	Incidence of Serious Adverse Events by System Organ Class, Preferred Term, and Grade
	Incidence of TEAE Related to Study Treatment
	Incidence of Serious TEAE Related to Study Treatment
	Incidence of TEAE Leading to Study Discontinuation
	Incidence of TEAE Leading to Study Drug Reduction
	Incidence of TEAE Leading to Study Drug Hold
	Incidence of Grade 3 or 4 TEAE by Preferred Term
	Incidence of Grade 3 or 4 TEAE by System Organ Class, and Preferred Term

	Summary of Death
Laboratory	Mean and Mean Change from Baseline in Numeric Laboratory Data: Hematology/ Clinical Chemistry/Coagulation/Urinalysis
	Frequency Table of Clinically Significant Laboratory Data: Hematology/ Clinical Chemistry Coagulation//Urinalysis
	Shift from Baseline in Laboratory Data: Hematology/ Clinical Chemistry/ Coagulation/Urinalysis
PK	Summary of Plasma Concentration of Milademetan by Scheduled Time Point
	Summary of PK parameters of Milademetan
Vital Signs	Mean and Mean Change from Baseline in of Vital Signs Data
	Frequency Table of Clinically Significant Vital Signs Data
Physical Exam	Summary of Physical Examination
ECG	Mean and Mean Change from Baseline in ECG Data
	Frequency Table of Clinically Significant Values in ECG
Liver Function	Summary of Liver Function Parameters for Potential Hy's Law
ECOG	Summary of ECOG by Visit

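### Laboratory grades are tabulated visit by visit with no worst post-baseline grade per patient, so the laboratory tables can understate how many patients ever reach Grade 3-4, especially for blood counts

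*SAP*

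**What the plan says.** SAP 6.5.3 plans three laboratory summaries:

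- Values and changes: "Laboratory data will be summarized in tables using descriptive statistics for baseline and each cycle/visit".
- Abnormalities: "clinically significant abnormalities in laboratory results will be summarized for the post-baseline cycles/visits using frequencies and percentages". The text does not say whether a patient is counted once overall or once at each visit.
- Grades: "Shifts in CTCAE grade between baseline and subsequent visits will be summarized as well".

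The matching entry in SAP section 8 is titled "Shift from Baseline in Laboratory Data: Hematology/ Clinical Chemistry/ Coagulation/Urinalysis". It mentions no worst or maximum grade. The data listings in SAP section 10 contain no laboratory listing apart from potential Hy's Law cases.

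SAP 6.5.6 treats liver tests differently. It plans on-therapy peak bilirubin against peak AST or ALT, and a Hy's Law listing that covers the whole study.

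Protocol 8.9 says laboratory results "must be resulted and evaluated prior to administration of the study drug", and that the listed variables "will be collected in accordance with the Schedule of Events" (Table 1, which is not in the text available for review). It also says "All clinically significant unscheduled laboratory results will be recorded", and the same sentence goes on to make every clinically significant result, scheduled or unscheduled, a reportable adverse event. The SAP section on adverse events then counts patients with Grade 3 or 4 treatment-emergent events, as graded by the investigator.

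**The concern.** For a safety conclusion, a reader wants to know how many patients ever reached Grade 3 or 4 in platelets, neutrophils or haemoglobin while on the drug. A table of shifts from baseline to each later visit answers a different question: how many were at that grade on a given visit. Patients who are severe at different visits cannot be added up from such tables, because the tables do not show whether they are the same people. An unscheduled value also has no natural cell in a by-visit layout.

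This matters most for blood counts. The SAP accepts the peak-value principle for liver tests but has no equivalent for haematology. Yet the plan anticipates haematological events: Protocol 6.12 allows filgrastim, and the SAP separates out serious events not associated with transfusion. In a single-arm, open-label study, a grade calculated from the laboratory value has the further merit of not depending on anyone's judgement of significance.

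**Working it through.** The documents give no laboratory toxicity rate, so there is no figure of the plan's own to reproduce. The check has two parts.

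**1. Which planned output gives a per-patient count of severe laboratory values?**

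| Output | Counts each patient once? | Depends on judged significance? |
|---|---|---|
| Grade shifts (SAP 6.5.3) | No, by subsequent visit | No |
| Clinically significant abnormalities (SAP 6.5.3) | Not stated | Yes |
| Peak liver tests and Hy's Law listing (SAP 6.5.6) | Yes, liver tests only | No |
| Grade 3 or 4 treatment-emergent events (SAP 6.5.2 on adverse events, SAP 8) | Yes | Yes, for laboratory findings (Protocol 8.9) |

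Outside liver tests, no row has "Yes" in the second column together with "No" in the third. Protocol 8.9 illustrates clinical significance with Grade 2 or higher AST, ALT or bilirubin and gives no example for blood counts.

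**2. How far can by-visit shares lie below the share ever affected?**

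Inputs: N = 65 (Protocol 4.1). The rate p at each visit and the number of visits k are assumptions. Everyone is assumed to attend every visit.

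- Same patients abnormal each time (lower bound): share ever affected = p.
- Independent visits: 1 − (1 − p)^k.
- Different patients at each visit (upper bound): min(1, k × p).

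For p = 3% and k = 8: the lower bound is 3% (65 × 0.03 = 1.95, about 2 patients). Independence gives 1 − 0.97^8 = 21.6% (65 × 0.216 = 14.0, about 14 patients). The upper bound is 8 × 3% = 24% (65 × 0.24 = 15.6 patients). Each single visit would show about 2 of 65 in all three cases.

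| p per visit (k = 8) | Same patients | Independent | No overlap |
|---|---|---|---|
| 1% | 1% | 7.7% | 8% |
| 3% | 3% | 21.6% | 24% |
| 5% | 5% | 33.7% | 40% |

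Fewer visits narrow the gap: at p = 5%, independence gives 14.3% for k = 3 and 26.5% for k = 6.

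Severe values seen only between visits would add to this. If v is the share with a severe value at some visit and u is the share of the remaining patients with one only off-visit, the total is v + (1 − v) × u. With v = 20% assumed, u = 5%, 10% or 20% gives 24%, 28% or 36%.

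Without full attendance, the number of patients at Grade 3-4 at one visit still cannot exceed the number ever affected. A percentage of those still attending can lie on either side of the patient-level share, because its denominator shrinks.

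**The case against.** The strongest reply is that the plan already has a per-patient table of severe toxicity. Clinically significant laboratory results become adverse events whether or not the sample was scheduled, they are collected up to 30 days after the last dose, or until another anticancer therapy starts if that comes first (Protocol 8.2.1), and patients with Grade 3 or 4 events are counted. Liver tests also have their peak analysis. This stands, and it narrows the point considerably. A reader might infer that unscheduled values are lost. For clinically significant results, Protocol 8.9 says the opposite. Nor does that section say that other unscheduled results are not recorded, and Protocol 12.1 asks for all study data to be entered. What remains is a severe value that the investigator does not judge clinically significant: it need not become an adverse event, and no table outside the liver tests counts it per patient.

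A reader might also infer that nadirs are missed, because results must be in hand before dosing and the last dose of one course is 12 days before the first dose of the next (Day 3 to Day 15, and Day 17 to Day 29, which is Day 1 of the next cycle). The documents do not support this. A pre-dose requirement does not make pre-dose samples the only ones, Table 1 is not visible, and no nadir timing is given.

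Finally, part of SAP 6.1 is redacted and could hold a rule on unscheduled or worst values. That cannot be excluded. However, the visible text of 6.1 gives precedence to a specific section where it departs from the general conventions, and 6.5.3 specifies shifts to subsequent visits.

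**Conclusion.** The point holds for the laboratory tables. As visibly written, they do not show how many patients ever reached a laboratory-derived Grade 3-4 outside the liver tests, and they can understate that share. The gap runs from nothing, if the same patients are abnormal at every visit, to large: 3% against 21.6% under independence and at most 24%, for an assumed 3% rate at 8 visits with full attendance. Both the rate and the number of visits are assumptions, and the true size cannot be derived from the documents.

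Two stronger conclusions are not supported. The study's safety reporting as a whole is not shown to understate severe toxicity, because the adverse event tables cover clinically significant results. And the by-visit percentages are not necessarily low at every visit once patients leave. This is a weakness in a descriptive analysis and has no bearing on sample size or on the efficacy analysis.

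**What to change.** In SAP 6.5.3, and under the shift-table entry in SAP 8, make the main table baseline CTCAE grade against worst post-baseline grade, with each patient counted once per laboratory variable. Use all recorded scheduled and unscheduled values from first dose to 30 days after last dose. Include the end-of-treatment sample even if it is drawn later within its window: Protocol 6.10 sets that visit at 30 days ± 7, so it can fall as late as day 37 (30 + 7), and a strict 30-day cut would drop it. Where CTCAE grades a variable for both low and high values, show the two directions separately. Keep the by-visit tables as supportive, and state how unscheduled values enter them. If the redacted part of SAP 6.1 already has such a rule, refer to it from 6.5.3.

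The cost is one derived variable and one table. No change to data collection under Protocol 8.9 is needed, since the table uses what is recorded.

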6.5.4 Vital Signs and Physical Examinations

[figure not shown]
Vital signs, including systolic and diastolic blood pressure, heart rate, and body temperature, as well as respiration rate will be collected each visit.

Summary tables will include descriptive statistics (number of patients, mean, std, median, Q1, Q3, min, and max) for baseline and each cycle/visit. Descriptive statistics will be calculated on both the actual value and the change from baseline.

Physical examination results will be summarized, and the frequency of clinically significant changes will be tabulated.

6.5.5 Electrocardiograms

The ECG will include heart rate, RR, PR, QRS, and QT intervals. The ECG will be read and interpreted at the investigational site for patient safety monitoring.

All ECG parameters, their change from baseline, and the frequency of abnormal ECG events will be summarized across study time points using descriptive statistic.

6.5.6 Liver Function Test Results

A listing will be generated for patients potentially meeting Hy's Law criteria (total bilirubin \geq (2xULN) and AST or ALT $>$ (3xULN) at any time during the study). Plots or tables of on therapy peak total bilirubin vs. peak AST (or ALT) will also be generated to help identify potential Hy's Law cases.

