5. SELECTION AND WITHDRAWAL OF PATIENTS

5.1. Inclusion Criteria

Each patient must meet all of the following criteria to be enrolled in the study:

[figure not shown]
1. Is \geq 18 years of age at the time of signing informed consent
2. Has signed and dated an informed consent form prior to the start of any study-specific qualification procedures
3. Has histologically and/or cytologically confirmed diagnosis of a cancer that is a locally advanced or metastatic solid tumor
4. Has measurable tumor lesion(s) in accordance with RECIST v1.1
5. Must have received all standard therapy appropriate for their tumor type and stage of disease or, in the opinion of the Investigator, would be unlikely to tolerate or derive clinically meaningful benefit from appropriate standard-of-care therapy

6. Has resolution of any clinically relevant toxic effects of prior chemotherapy, surgery, radiotherapy, or hormonal therapy

[figure not shown]

7. Presence of WT *TP53* and *MDM2* gene amplification by tumor tissue/blood testing, defined as:
 - a. ≥ 8 copies in tumor tissue by central laboratory or
 - b. ≥ 8 copies or 4-fold increase in tumor tissue or blood by local testing

8. Has an ECOG performance status of 0 or 1
9. Has adequate bone marrow function, defined as:
 - a. Platelet count $\geq 100 \times 10^9/L$
 - b. Hemoglobin $\geq 9.0 \text{ g/dL}$
 - c. Absolute neutrophil count $\geq 1.5 \times 10^9/L$
10. Has adequate renal function, defined as creatinine clearance $\geq 30 \text{ mL/min}$, as calculated using the modified Cockcroft-Gault equation (or equivalent glomerular filtration rate calculated using the Chronic Kidney Disease Epidemiology Collaboration formula)
11. Has adequate hepatic function, defined as:

- a. Alanine aminotransferase and aspartate aminotransferase $\leq 3 \times$ the ULN if no liver metastases are present or $\leq 5 \times$ ULN if liver metastases are present
- b. Total bilirubin $\leq 1.5 \times$ ULN or $\leq 3 \times$ ULN in the presence of liver metastases. Patients with Gilbert's disease who have serum bilirubin levels of $> 3 \times$ ULN may be enrolled
12. Is willing and able to comply with the protocol requirements
13. If requiring anticoagulation medication, should be on a stable regimen, defined as being on the same dose for at least 4 weeks

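### The potential Hy's Law listing has no post-first-dose limit, baseline reference or pairing window, so an eligible patient with liver metastases can be flagged without any drug effect

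*SAP*

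**What the plan says.** SAP 6.5.6 describes two outputs with different time frames.

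- **The listing.** "A listing will be generated for patients potentially meeting Hy's Law criteria", defined as total bilirubin ≥2×ULN and AST or ALT >3×ULN, "at any time during the study".
- **The display.** "Plots or tables of on therapy peak total bilirubin vs. peak AST (or ALT) will also be generated", as a help in finding potential cases. This one is limited to on-therapy values.

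The end of the first sentence and the start of the second stand side by side as "at any time during the study). Plots or tables of on therapy peak total bilirubin vs. peak AST (or ALT", so the change of time frame is easy to overlook.

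Neither output is given a window between the bilirubin and the transaminase elevation, and neither refers to baseline. SAP 8 plans a table titled "Summary of Liver Function Parameters for Potential" Hy's Law, and SAP 10 plans a listing of potential cases.

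Protocol 5.1, criterion 11, sets the entry limits. AST and ALT may be up to 3×ULN, or up to 5×"ULN if liver metastases are present". Total bilirubin may be up to 1.5×ULN, or up to 3×"ULN in the presence of liver metastases". Patients with Gilbert's disease may enter with bilirubin above 3×ULN. Protocol 8.9, Table 6, includes "Alkaline phosphatase" among the chemistry tests, but SAP 6.5.6 does not use it.

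**The concern.** A potential Hy's Law flag is meant to draw attention to possible drug-induced liver injury. Here the entry limits for patients with liver metastases lie above both thresholds of the flag. The listing rule does not separate a value that was there before treatment from one that arose on it.

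The missing time link is a second source of false flags. A transaminase rise in an early cycle and a bilirubin rise at hepatic progression months later satisfy the listing as it is most naturally read. For the display, pairing peak with peak is explicit. Limiting that display to on-therapy values does not fully prevent this, because Protocol 6.4 allows treatment beyond progression.

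The trial has a single arm, so there is no control rate against which to judge background flags. If the SAP does not say how such flags are handled, someone will have to decide which ones count after seeing the data. The SAP already defines a time window for adverse events (first dose to 30 days after the last dose), but 6.5.6 does not use it.

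**Working it through.** The plan gives no figure to reproduce. The check compares the entry limits with the flag thresholds, then tests the pairing rule on a small example.

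**Inputs** (multiples of ULN)

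| Patient group | AST/ALT allowed at entry | Bilirubin allowed at entry |
|---|---|---|
| No liver metastases | ≤3 | ≤1.5 |
| Liver metastases | ≤5 | ≤3 |
| Gilbert's disease | as above, by liver metastases | >3 allowed |

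Flag (SAP 6.5.6): AST or ALT >3 **and** bilirubin ≥2.

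**Step 1. Can an eligible patient meet both limbs at entry?**

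- *No liver metastases, no Gilbert's disease.* AST/ALT ≤3 fails >3, and bilirubin ≤1.5 fails ≥2. Neither limb can be met.
- *Liver metastases.* AST/ALT above 3 and up to 5, with bilirubin from 2 to 3, is eligible and meets both limbs. Example: AST 4×ULN with bilirubin 2.5×ULN.
- *Gilbert's disease with bilirubin above 3×ULN, no liver metastases.* The bilirubin limb is met, but AST/ALT is capped at 3 and the rule needs more than 3. Only one limb is met at entry.
- *Gilbert's disease with liver metastases.* Both limbs can be met.

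A grid in steps of 0.1×ULN confirms the first two lines. Without liver metastases, 30 × 15 = 450 eligible combinations, of which 0 meet both limbs. With liver metastases, 50 × 30 = 1,500 eligible combinations, of which 20 × 11 = 220 meet both, running from (3.1, 2.0) to (5.0, 3.0). These counts show that the overlap exists. They are not probabilities, because patients are not spread evenly over the grid.

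**Step 2. Does the pairing rule matter?** Take one patient with two visits:

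| Visit | AST | Bilirubin | Both limbs at this visit? |
|---|---|---|---|
| 1 | 4.0 | 0.8 | no |
| 2 | 1.0 | 2.2 | no |

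- Any-time rule: maximum AST 4.0 > 3 and maximum bilirubin 2.2 ≥ 2, so the patient is flagged.
- Same-visit rule: no visit meets both, so the patient is not flagged.

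**Step 3. Size.** With about 65 patients planned, one flag is 1/65 = 0.0154, or 1.5 percentage points if the flags are reported as a proportion. The number of false flags would need the share of patients with liver metastases and the joint distribution of their baseline liver tests. The documents give neither.

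**The case against.** The strongest reply is that this is a screening list of potential cases and is meant to be sensitive. That stands, and it sets the weight of the point. A reader might infer that the loose rule could hide a real case. It cannot do so by omission: every patient caught by a post-first-dose, same-sample rule is also caught by the any-time rule. The error is extra rows to review.

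Several other replies deserve an answer.

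- **Screening values may not be meant.** Protocol 6.1 counts a patient as enrolled at the first dose, so the phrase about the study could be read to exclude screening. That reading is possible, but it does not remove the problem. A patient who stays at AST 4×ULN and bilirubin 2.5×ULN is flagged at the first post-dose sample with no change from baseline.
- **The listing could mean both limbs met together at some time.** The wording allows this, although no window is stated. Saying so in the SAP would settle it.
- **Redacted conventions may cover it.** Part of SAP 6.1 is blacked out, but the visible text says that conventions in the specific sections take precedence, so 6.5.6 governs its own time frame.
- **Baseline is handled elsewhere.** SAP 6.5.3 gives changes from baseline and shifts in CTCAE grade, and investigators assess causality of adverse events. These help a reader, but they are not linked to this listing and are not described as joint for bilirubin and transaminases.

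Two further readings go beyond the text. One is that the screening problem also affects the plots or tables; it does not, because they use on-therapy values. The other is that false cases will be counted in the planned summary table. Only its title is visible, and nothing says that it counts patients by the any-time rule.

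**Conclusion.** The point holds as a low-cost improvement to a descriptive safety output. As written, the listing rule can be met by an eligible patient with liver metastases with no drug effect, and it can join elevations that occurred at different times. The consequence is false-positive flags that are hard to interpret without a control arm. ORR and the other efficacy endpoints are untouched.

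The size in patients cannot be stated. A reader might assume that 30% to 40% of 65 have liver metastases (about 20 to 26 patients) and that 5% to 10% of those lie in the overlap at entry, which gives 1.0 to 2.6 patients. Both shares are assumptions without support in the documents, and the true number could be zero. What can be derived is the overlap region itself and the 1.5 percentage points per flag, the latter only if flags are reported as a proportion of 65.

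**What to change.** Amend SAP 6.5.6 before database lock:

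1. Keep the broad any-time list, labelled as a screen.
2. Base the reported potential Hy's Law cases on values after the first dose.
3. Add a flag for whether the bilirubin rise was on the same sample as the AST/ALT rise or within a pre-specified number of days after it. Choose that number with the laboratory schedule in view.
4. Show baseline AST, ALT, bilirubin and alkaline phosphatase in the listing, with liver-metastasis and Gilbert's status where recorded.
5. Identify separately the patients already above either threshold at baseline, and give their later values as multiples of baseline.
6. State which of these rules the planned Hy's Law table uses.

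The cost is SAP wording and a little programming. The four laboratory tests are already collected. Liver metastases are not among the baseline characteristics in SAP 6.3.2 (brain metastases are), so that status and Gilbert's disease may have to be taken from tumor or medical-history records. The narrower flag could miss a case whose samples were widely spaced; the retained broad list covers that.
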